Background and rationale	
With the rise of cardiovascular diseases (CVD) and diabetes, the global disease burden is shifting towards non-communicable diseases (NCDs). An increasing number of low- and middle-income countries (LMICs) are currently experiencing the double burden of infectious and non-communicable diseases. In order to facilitate a patient-centred approach to healthcare, there is an urgent need to ensure that primary healthcare (PHC) facilities in LMICs are capable of addressing diagnosis and monitoring of non-communicable diseases at the point-of-care (POC). Important minimum parameters for PHC POC diagnosis and monitoring of cardiometabolic diseases are lipids/lipoproteins, glucose, glycated haemoglobin (HbA1c) and serum creatinine, to address cardiovascular disease, diabetes and chronic kidney disease.
 
While several technologies of multi-parameter POC devices capable of supporting diagnosis and monitoring of cardiometabolic diseases exist, their quantitative accuracy is often not well evaluated outside of the manufacturer's laboratories and published independent evaluations can be rare, particularly in the settings of intended use. These settings are PHC facilities in varying climatic environments and with staff without specialist laboratory training. Our study aims to evaluate the quantitative accuracy of 2 cardiometabolic POC devices (the SimplexTAS 101 from Tascom and the Aina Station from JanaCare) in a setting of intended use and performed by the intended user.

Primary objective(s)	1.1. To determine the accuracy of quantitative measurements of glucose, HbA1c, total cholesterol and creatinine as measured in a healthcare setting with point-of-care multiparameter devices compared to a laboratory reference method
Secondary objective(s)	2.1 To evaluate the operational characteristics and system usability of each cardiometabolic device when used in a PHC setting
Primary endpoints (outcomes)	
1.1. Estimates of correlation and linear dependence between quantitative measurements of glucose, HbA1c, total cholesterol and creatinine evaluated in a healthcare setting with point-of-care multiparameter devices and in a laboratory reference assay.
 
1.2. Estimates of accuracy and limits of agreement for quantitative measurements of glucose, HbA1c, total cholesterol and creatinine evaluated in a healthcare setting with point-of-care multiparameter devices (compared to a laboratory reference assay).

Secondary endpoints (outcomes)	
2.1 Operational characteristics and usability of study devices:
 
 - Rate of invalid test results and error types - System usability score
Study design	Prospective quantitative accuracy study
Study sites/setting	Multi-centre: Dhulabari Primary Healthcare Centre, Kakarvitta Health Post, Nepal
Study population	Members of the local community attending the facility under the KHDC program
Sample Size	400
Eligibility criteria	Age: ≥ 20 years; KHDC clinic attendees; Hb ≥ 8 g/dL; Consenting
Study duration	4 months
Time schedule	Anticipated start Q1 2022

Schedule of Activities

Procedure	Daily (working days)	Weekly	Notes
Eligibility assessment	X		excluding haemoglobin testing
Informed consent	X		-
Haemoglobin testing	X		-
Demographic information	X		-
Fingerstick testing	X		-
Venous sample collection	X		-
Venous sample transport to reference lab	X		-
Reference lab testing	X		-
Data entry		X	-

1 Introduction

With the rise of cardiovascular diseases (CVD) and diabetes, the global disease burden is shifting towards non-communicable diseases (NCDs). An increasing number of low- and middle-income countries (LMICs) are currently experiencing the double burden of infectious and non-communicable diseases [1]. CVD and diabetes alone make up more than two thirds of the global burden of the four most common NCDs, including chronic respiratory diseases and cancer [2]. In order to facilitate a patient-centred approach to healthcare, there is an urgent need to ensure that primary healthcare (PHC) facilities in LMICs are capable of addressing diagnosis and monitoring of both infectious and non-communicable diseases at the point-of-care.

In 2020 the Foundation for Innovative New Diagnostics (FIND), together with technical inputs from the World Health Organization (WHO), developed a landscape of multi-parameter point-of-care (POC) devices capable of supporting diagnosis and monitoring of cardiometabolic diseases at PHC facilities [3]. Cardiometabolic risk factors include raised blood pressure, raised blood glucose, raised blood lipids, excess weight and obesity. The WHO Package of Essential Noncommunicable Disease Interventions for primary health care in low resource settings (WHO PEN package, [4], as well as the WHO Model List of Essential In Vitro Diagnostics (EDL, [5]), include several parameters for the use at POC that should be used to detect and manage cardiometabolic risk. These include lipids/lipoproteins, glucose, glycated haemoglobin (HbA1c) and serum creatinine, to address cardiovascular disease, diabetes and chronic kidney disease.

Together with a range of clinical and laboratory experts, FIND developed a target product profile (TPP) for cardiometabolic POC devices, with the aim to define the minimal and optimal requirements for such devices in PHC settings in LMICs [6]. Beyond the test menu available, requirements considered related to device design, usability, storage and operating temperature, data management and affordability.

The diagnostic devices identified in the landscape were evaluated against the TPP requirements and in discussion with experts, to evaluate which of the devices meet minimal and optimal requirements, with the aim to select two devices for a quantitative accuracy and system usability evaluation.

1.1 Study Rationale

While several technologies of multi-parameter POC devices capable of supporting diagnosis and monitoring of cardiometabolic diseases exist, their diagnostic accuracy is often not well evaluated outside of the manufacturer's laboratories and published independent evaluations can be rare, particularly in the settings of intended use. These settings are PHC facilities in varying climatic environments and with staff without specialist laboratory training.

Our study aims to evaluate the diagnostic accuracy of two cardiometabolic POC devices in a setting of intended use and performed by the intended user. The results will generate evidence on the expected accuracy of these POC devices and their performance in comparison to a standard laboratory method.

1.2 Background

Independent performance evaluation of POC devices have shown that many devices, regardless of their intended use, do not perform as well as the manufacturers' claims may suggest [7, 8]. There are a variety of reasons for this, including difference in skills levels of personnel who were involved in generating the data for the manufacturer's claims and who actually perform the test in a clinic, limited evaluation of samples from different geographical locations and thus potential interfering substances or less controlled environmental conditions (e.g. dust, heat and humidity).

Independent performance evaluations to assess clinical accuracy, as well as system usability are important to drive adoption of any technology, and even more so, if the technology is intended to move testing outside of the traditional setting, i.e. away from the central laboratory to the point-of-care. Many devices appear ideally suited for certain settings, however when it comes to actual implementation, the users often discover that the device and workflow do not meet their needs. The choice of a suboptimal device means badly invested resources and may lead to inappropriate use, resulting in fewer reliable tests for patients in the absence of alternatives. Data from real-world evaluations in settings of the intended use can support decision makers to select the right device.

The setting for this study will be a primary healthcare facility and a health post in Nepal, where study participants attend the facility in the context of the "Early detection and management of Chronic Kidney Diseases, Hypertension, Diabetes and Cardiovascular disease in Community in Nepal (KHDC-Nepal) program", conducted by the University Hospital of Geneva and the B.P. Koirala Institute of Health Science in Nepal.

1.3 Benefit/Risk Assessment

The risks for study participants are minimal as the study procedures only include collection of fingerstick blood and venous blood. Participants are facility attendees in the context of the above mentioned KHDC-Nepal early detection program, under which they have access to the relevant healthcare related to any clinical findings from this diagnostic accuracy study.

2 Study Objectives and Endpoints

TABLE 1: STUDY OBJECTIVE AND ENDPOINTS

Objectives	Endpoints
Primary	
1.1 To determine the accuracy of quantitative measurements of glucose, HbA1c, total cholesterol and creatinine* as measured in a healthcare setting with point-of-care multiparameter devices compared to a laboratory reference method.	
1.1. Estimates of correlation and linear dependence between quantitative measurements of glucose, HbA1c, total cholesterol and creatinine evaluated in a healthcare setting with point-of-care multiparameter devices and in a laboratory reference assay.
 
1.2. Estimates of accuracy and limits of agreement for quantitative measurements of glucose, HbA1c, total cholesterol and creatinine

	evaluated in a healthcare setting with point-of-care multiparameter devices (compared to a laboratory reference assay).
Secondary	
2.1 To evaluate the operational characteristics and system usability of each cardiometabolic device when used in a PHC setting	
2.1 Operational characteristics and usability of study devices:
 
 - Rate of invalid test results and error types - System usability score

*note: Creatinine is only available for one of the two investigational products

3 Study Design

3.1 General Design

This is a prospective quantitative accuracy study to assess the performance of clinical chemistry POC devices in comparison to a standard state of the art laboratory reference method available in the study country.

The general study concept is shown in Figure 1. For more information on the investigational product see section 4.1. Note that creatinine on the Aina Jana Care cardiometabolic platform is still in development and not available for evaluation.

FIGURE 1: STUDY CONCEPT, PARAMETERS EVALUATED AND REFERENCE TESTS

Study concept		
Investigational products		Reference tests
SimplexTAS 101	Jana Care	Roche Cobas lab test
Glucose	✓ Enzymatic (GOD)	✓ Enzymatic (GDH)
HbA1c	✓ Enzymatic	✓ Boronate affinity
Total cholesterol	✓ Enzymatic	✓ Enzymatic
Creatinine	✓ Enzymatic	n/a
Test concept	Cartridge-based liquid chemistry	Bulk-reagent liquid chemistry
	Strip-based dry chemistry	Immunoassay

3.2 Scientific Rationale for Study Design

The study design was chosen with the objective in mind to evaluate the performance of POC devices compared to standard laboratory methods. In most countries, standard of care testing of the assessed parameters is done in centralized laboratories using venous whole blood. POC methods have several advantages over centralized methods, in that they use simpler sampling collection methods, i.e. fingerstick whole blood, do not require sample transport networks and can deliver results while the patient is at the healthcare facility. However, their adoption is often hampered by the perception that POC devices are less accurate, compared to centralized laboratory methods and the only comparison data available are generated by the manufacturers.

3.3 End of Study Definition

A participant is considered to have completed the study if he/she has completed the visit and all procedures as shown in the Schedule of Activities. The end of the study is defined as the date when all data entry is completed in the clinical study data base.

3.4 Study Population and Eligibility

The study will be conducted in two sites, at the Dhulabari primary healthcare centre (PHC) and at the Kakarvitta Health post in the rural area of Jhapa in Eastern Nepal. The study will be embedded in the KHDC-Nepal program, which has the objective to improve the health of the Nepalese population in Eastern Nepal through early detection and management of chronic non-communicable diseases. The program runs community awareness sessions and door-to-door visits to encourage members of the community to attend a screening visit at selected primary health facilities, health posts or at a pre-designated location. During this visit, people are screened for hypertension, diabetes, chronic kidney and cardiovascular disease, including (but not limited to) testing for glucose, lipids, HbA1c and creatinine.

Focus of the program are individuals ≥ 40 years of age based on the WHO risk prediction chart [9] and anyone ≥ 20 years is eligible for screening. In the program region, 50% of the population above 40 is expected to be screened, in which 25% may have at least one non-communicable disease (e.g. diabetes or elevated blood pressure) [10]. Anyone who screens positive for the NCDs in focus of the program is linked or referred to care at their local healthcare facility.

Community members who attend the Dhulabari PHC facility and the health post Kakarvitta in the context of the KHDC program will be invited to participate in the present study until the daily recruitment target across both sites is reached (5 participants per site/per day, or more if the site has capacity to test more participants per day). The Dhulabari PHC facility and the Kakarvitta health post run screening activities for the KHDC program during three hours in the morning. If interested and eligible study participants cannot be tested during these hours, they will be given appointments on a first-come-first-served basis for study participation. Additionally, KHDC program participants can be enrolled if they visit the Dhulabari PHC facility or Kakarvitta health post for a follow up appointment.

Results generated with the investigational products, or the reference assay will not be used for clinical decision making as the participants will have received these screening tests in the context of the KHDC program.

During the eligibility procedure, potential study participants will also be tested for haemoglobin to investigate if they suffer from abnormal haemoglobin values, which may have an impact on their HbA1c levels [11]. If potential participants are found to have haemoglobin levels of <8 g/dL, they will not be eligible for the study and will be referred by the local physician for follow up care.

Prospective approval of protocol deviations to recruitment and enrolment criteria, also known as protocol waivers or exemptions, is not permitted.

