3.5 Inclusion Criteria

Participants are eligible to be included in the study only if all of the following inclusion criteria apply:

- 20 years or older (in line with KHDC eligibility age)
- Attending the Dhulabari PHC facility or Kakarvitta health post in the context of the KHDC program
- Haemoglobin levels ≥8 g/dL
- Able and willing to provide informed consent

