3.6 Exclusion Criteria

Participants are excluded from the study if any of the following exclusion criteria apply:

- Inability to provide sufficient capillary or venous whole blood sample for all tests
- Haemoglobin levels < 8g/dL
- Anyone attending the Dhulabari PHC facility or Kakarvitta health post for other reasons than the KHDC program

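### Section 3.4 bars all clinical use of reference-assay results on a premise that eligibility does not enforce, conflicts with section 1.3, and leaves no stated route for a critical result that is new to KHDC

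*Protocol*

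**What the plan says.** Section 3.4 embeds the study in the KHDC-Nepal screening program. It describes the KHDC visit as covering glucose, lipids, HbA1c and creatinine, and says of those found to have disease: "Anyone who screens positive for the NCDs in focus of the program is linked or referred to care at their local healthcare facility".

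The same section states that study results, from the reference assay as well as from the investigational devices, "will not be used for clinical decision making as the participants will have received these screening tests in the context of the KHDC program". No exception is given.

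On who may enter, section 3.5 asks for "Attending the Dhulabari PHC facility or Kakarvitta health post in the context of the KHDC program", and section 3.6 excludes "Anyone attending the Dhulabari PHC facility or Kakarvitta health post for other reasons than the KHDC program". Section 3.4 adds that "KHDC program participants can be enrolled if they visit the Dhulabari PHC facility or Kakarvitta health post for a follow up appointment".

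Section 1.3, in assessing risk as minimal, says of participants in KHDC that "they have access to the relevant healthcare related to any clinical findings from this diagnostic accuracy study".

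One study measurement has a stated clinical consequence. For people with haemoglobin below 8 g/dL, section 3.4 says "they will not be eligible for the study and will be referred by the local physician for follow up care".

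**The concern.** The bar in 3.4 is sensible for the investigational devices, whose accuracy is the question under study. It is harder to defend for the reference assay. That is the laboratory standard against which the devices are judged, and section 11 has the sponsor verify the laboratory's quality procedures before the study starts.

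The sole reason given for the bar is that KHDC has already supplied the same information. Where that is true, little is lost. Where it is not, staff who follow 3.4 have an instruction against clinical use of a critical reference glucose or creatinine, while 1.3 points to care for what the study finds. The two sections need to agree, because 6.8 and 8.2.2 both refer back to 1.3 to justify having no safety assessments and no safety analysis.

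What is at stake is the safety of individual participants and the consistency of the protocol. The statistical results are not at stake.

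**Working it through.** No arithmetic applies beyond a count. The check sets the relevant sections side by side.

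**1. Scope of the bar.** Section 3.4 covers both device and reference results and carries no exception for critical values.

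**2. Is the premise secured?** Section 3.5 lists 4 inclusion criteria (age, attendance in the KHDC context, haemoglobin of at least 8 g/dL, consent). Section 3.6 lists 3 exclusion criteria (insufficient blood sample, haemoglobin below 8 g/dL, attendance for other reasons). Of these 4 + 3 = 7 criteria, 0 require a completed KHDC test and 0 set an interval since one. Two of the seven concern KHDC, and both concern attendance only.

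**3. Can time pass between the KHDC test and study entry?** Yes. Section 3.4 permits enrolment at a KHDC follow-up appointment and sets no maximum interval.

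**4. Would the study data show that a result is new to KHDC?** Section 6.1 takes the KHDC screening diagnosis from the medical record. That item presupposes that screening took place, which supports the premise in part. The KHDC laboratory values and their dates are not among the listed items, so the listed data would not show whether a reference result is new or discordant.

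**5. Is there a route for a critical reference result?**
- Section 3.4: referral for low haemoglobin only, in people who are then not enrolled. None of the four reference markers (glucose, HbA1c, total cholesterol, creatinine) has an equivalent.
- Section 6.8: no safety assessments are planned.
- Section 7: among adverse events, only deaths within the study visit are recorded and reported.
- Section 9.1: significant safety findings go to the ethics committee, which is oversight and not clinical referral.
- Section 10.1: reference results are transcribed to the paper case report form.

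**6. Do 1.3 and 3.4 agree?** Section 1.3 says care is accessible for this study's clinical findings. Section 3.4 says the study's results do not inform clinical decisions. The two can both hold when KHDC already has the same result and has referred the person. They cannot both hold when the finding comes only from the study's reference assay.

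**7. Size.** The protocol gives no rate of critical results, no rate of discordance between KHDC and reference results, and no share of participants entering at follow-up visits. The number affected cannot be estimated, and none is assumed here.

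**The case against.** The strongest case against is that the embedded design already secures what the criteria leave unsaid. KHDC attendance is required, the KHDC visit is described as testing the same markers, positives are referred, and 6.1 presupposes completed screening. People enrolled at follow-up are already in contact with the program. The reference laboratory belongs to the institute that co-conducts KHDC (sections 1.2 and 6.3.2). The Study Manual, consent pages and study-flow figure are not available to this review and may contain a route. Section 3.4 also does not expressly forbid telling a clinician.

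Most of this stands, and it is why the point is small. It does not remove the conflict. Ordering a repeat test because of a reference result is itself a clinical decision based on that result, and 3.4 bars this without exception, so a route in another document would still sit against its wording. Section 1.3 describes access to care; it gives nobody the task of passing a result on.

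Two stronger readings are tempting and are not supported:
- A reader might infer that critical results will be ignored. The protocol does not direct that throughout: 1.3 points the other way, and KHDC testing and referral run in parallel.
- A reader might infer that the overflow arrangement, under which "they will be given appointments on a first-come-first-served basis for study participation", produces outdated KHDC results. Those appointments arise because screening runs for three hours in the morning, and nothing suggests a long delay. Only the follow-up route leaves the interval open.

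**Conclusion.** The point holds in a limited form and is worth considering. Section 3.4 bars all clinical use of reference results on an assumption that none of the seven eligibility criteria enforces. The bar conflicts with 1.3, and the protocol states no route by which a critical reference glucose or creatinine reaches the KHDC clinician. The gap is confined to critical results that are new to KHDC or disagree with its result.

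This rests on two assumptions: that KHDC testing and referral work as described for most participants, and that the material not available here does not already amend 3.4. If the Study Manual has a route, what remains is a wording conflict that a cross-reference and a stated exception would resolve. The matter does not belong to a statistical analysis plan, since the sentence in 3.4 is itself what needs changing. No endpoint, estimate or sample size is affected.

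**What to change.** Keep the bar on investigational-device results. After the sentence on clinical use in 3.4, add:

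> *Exception: a reference-laboratory result beyond the laboratory's own critical limits is reported to the site investigator when validated and passed to the KHDC clinician, who confirms it by repeat testing before treatment.*

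If the Study Manual already has such a route, 3.4 can state the exception by referring to it. Leave the wording of 1.3 as it is and add only a cross-reference to 3.4. Replacing its general statement with a closed list would narrow the care it now covers, for example for a raised creatinine short of the laboratory's critical limit.

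The cost is a short protocol amendment with ethics committee review (section 9.1), a matching sentence in the consent form if it lacks one, and occasional notifications and repeat tests. No new thresholds are needed, because the laboratory's own limits apply, and the enrolment log in 6.1 lets the site link a study ID to a participant.
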